#### **6.6.8 Laboratory Assessments**

There are no required laboratory tests for this registry. Laboratory tests, such as chemistry, hematology, and erythrocyte sedimentation rate (ESR), will be collected when part of the physician's site routine care. However to assess the PedACR score, it is recommended that CRP and/or ESR be provided where available. If available as part of routine care, anti-nuclear antibody (ANA) and past or current genetic testing results HLA-B27 will be collected. There is no central laboratory for this registry; therefore all lab assessments will be conducted by a local laboratory at the physician's discretion and collected where available.

### **6.6.9 Inactive Disease Assessment**

The inactive disease assessment will be recorded starting at the enrollment visit and at each registry visit thereafter through Year 5. A patient has inactive disease if he/she meets the following:

- No active arthritis
- No fever
- No rash
- No serositis
- No splenomegaly
- No generalized lymphadenopathy attributable to JIA
- No active uveitis in connection with JIA
- Normal ESR or CRP level only when part of the physician's site routine care
- Physician's global assessment of disease activity indicating clinical disease quiescence.

### **6.6.10 Assessment of JIA Associated Uveitis**

Data will also be collected for patients with uveitis in connection with their JIA (pre-registry onset and new onset of JIA associated uveitis during the registry participation) to determine how strongly it affects their ability to function normally through Year 5, as applicable.

For patients with JIA associated uveitis it is requested that the treating Rheumatologist obtains the assessment results from the patient's Ophthalmologist according to the local clinical practice for the following:

- Uveitis manifestation
- Uveitis localization
- Summarizing evaluation of uveitis by eye as:
  - No irritation

Less inflammation

No change in uveitis

More inflammation

compared to uveitis at prior registry visit (starting with registry visit after Baseline as applicable)

New/additional complications in uveitis since last registry visit (starting with registry visit after Baseline as applicable)

Actual Visual Acuity by eye

Anterior Chamber Cells

Vitreous Haze

#### **6.6.11 Humira and Methotrexate Treatment and Dosing Changes**

Prior to enrolling a patient into the registry, the participating Physician will provide the patient a prescription for Humira or MTX along with instructions for appropriate use. At each registry visit, the Physician will collect the start and stop dates (if applicable), any dose interruptions and reason for the dose interruption that may have occurred since the last registry visit. The dose, dates of administration, any dose interruptions or changes, and the reason for the interruption will be captured in the source documents and eCRFs. Humira and MTX registry treatments and dosing changes will be collected through registry Year 10.

#### **6.6.12 Product Supply**

AbbVie will not provide any medication or therapy for this registry. Patients will receive commercial product as prescribed by their treating physician.

#### **6.7 Effectiveness and Safety Assessments/Variables**

This is a long-term observational registry with the objective of documenting safety and effectiveness of Humira, using MTX as a reference, in routine clinical practice.

### 6.7.1 Effectiveness Variables

Information to evaluate the effectiveness of Humira or MTX therapy will be collected from patients and their physicians if part of routine clinical assessment. In the event Humira therapy is interrupted, effectiveness variables will be collected during the interruption.

The effectiveness of therapy evaluation provided by the patient or parent will be collected with clinical assessments as discussed in Section 6.6.6. The following clinical assessments will be used:

- Parent's Assessment of Patient's Pain (VAS)
- Parent's Global Assessment of Patient's Disease Activity (VAS)
- Physical function of the DICHAQ
- Child's Quality of Life CHQ-PF50

Effectiveness of therapy provided by the physician will be collected through the Physician's Global Assessments, if part of routine clinical assessment. The following assessments will be collected:

- Physician's Global Assessment of Disease Activity (VAS) ([Appendix F](#))
- Joint pain and swelling
- Number of active joints
- Number of joints with limitation of passive motion (LOM)
- Number of joints with pain on passive motion (POM)
- CRP and/or ESR level only when part of the physician's site routine care

Patients may also be evaluated for inactive disease. The criterion for inactive disease includes the following:

- No active arthritis
- No fever

No rash  
No serositis  
No splenomegaly  
No generalized lymphadenopathy attributable to JIA  
No active uveitis in connection with JIA  
Normal ESR and/or CRP level only when part of the physician's routine care  
Physician's global assessment of disease activity indicating clinical disease quiescence.

### **6.7.2 Safety Variables**

The physician will be asked to document SAEs and Adverse Events of Special Interest (AESI) on eCRFs (Section 7.0).

SAEs and Adverse Events of Special Interest (AESI) will be reported to AbbVie from the time the physician obtains the patient's authorization to use and disclose information (or the patient's informed consent/patient authorization) throughout the registry or Direct to HCP follow-up process until satisfactory conclusion or until 70 days following last dose of registry drug (whichever is longer). In the event Humira therapy is interrupted, SAEs and Adverse Events of Special Interest (AESI) will be collected throughout the interruption. If a patient switches from MTX to Humira treatment, SAEs and AEs of Special Interest will continue to be collected under the Humira arm. If treatment with Humira or MTX is permanently discontinued for any reason, patients will be discontinued from treatment and the reason for discontinuation will be recorded on the Study Drug Completion eCRF. Patients that discontinue treatment will be encouraged to remain in the registry and will be followed for safety and effectiveness through Year 5 and SAEs and AESI will be followed until satisfactory conclusion or until 70 days following last dose of registry drug (whichever is longer), and starting at Year 6, patients will be followed annually for the subset of AESI which include congestive heart failure and malignancies and SAEs through Year 10 of the registry until satisfactory conclusion or until 70 days following last dose of registry drug (whichever is longer). For polyarticular

JIA patients 2 to < 4 years of age in countries with available local approval for this group of patients at the time of consent to the registry the AESI and SAEs will be collected for the full 10 years as defined by the protocol (Figure 2) and will be followed up until satisfactory conclusion or until 70 days following last dose of registry drug (whichever is longer). Patients that discontinue from the Registry (before 10 years) will be offered to participate in the direct to HCP process as allowed by applicable local regulations. Safety data from these patients will be collected by completion of a simplified HCP questionnaire on an annual basis. The questionnaire focuses on the collection of Adverse Events of Special Interest, hospitalizations, surgeries, death and polyarticular JIA related medication use through Year 5 and malignancies, CHF, hospitalizations, surgeries and death from Year 6 through Year 10 (Figure 1). Polyarticular JIA patients 2 to < 4 years of age in countries with available local approval for this group of patients at the time of consent to the registry and participating in the HCP follow-up process will have AESI, hospitalizations, surgeries, death and polyarticular JIA related medication use collected for the full 10 years (Figure 2).

SAEs, Adverse Events of Special Interest (AESI), and pregnancies will be collected on their respective eCRFs (refer to Section 7.0 and Section 7.1.9 for details).

## **6.8 Removal of Patients from Therapy or Assessment**

### **6.8.1 Discontinuation of Individual Patients**

A patient may withdraw from the registry at any time without prejudice due to withdrawal of consent, lost to follow-up as defined below, or death.

If the Physician, for any reason, decides it is in the best interest of the patient to discontinue Humira or MTX, treatment should be stopped. A patient that discontinues Humira or MTX treatment will be encouraged to remain in the registry. Efforts will be made to follow all patients through Year 5 of the registry for safety and effectiveness and from Year 6 through Year 10 congestive heart failure, malignancies, pregnancies and SAEs. For polyarticular JIA patients 2 to < 4 years of age in countries with available local approval for this group of patients at the time of consent to the registry the AESI,

SAEs and pregnancy (potentially during the study at the age when patient can become pregnant) will be collected for the full 10 years as defined by the protocol (Figure 2). The following reasons, but not limited to, for treatment discontinuation should be noted on the eCRFs.

Clinically significant abnormal laboratory results or AEs, which prevent continuation of Humira (monotherapy or combination therapy with MTX) and/or MTX (monotherapy without Humira) as determined by the Physician.

The physician believes it is in the best interest of the patient.

The parent, legal guardian, or patient requests withdrawal from the registry.

The patient is lost to follow-up, i.e., does not provide data for 1 year and does not respond to notifications from the site.

The patient receives a concomitant biologic anti-rheumatic therapy other than Humira.

The patient is diagnosed with a malignancy except for localized non-melanoma skin cancer. Discontinuation for carcinoma-in-situ is at the discretion of the Physician.

Patients who interrupt their Humira or MTX therapy and do not restart within 1 year.

Lack of effectiveness.

Patients who have discontinued from the registry prior to Year 10 will be contacted to determine interest in participation in direct to HCP process that includes the HCP's completion of a simplified HCP questionnaire on an annual basis.

## **7.0 Complaints**

A Complaint is any written, electronic, or oral communication that alleges deficiencies related to the physical characteristics, identity, quality, purity, potency, durability, reliability, safety, effectiveness, or performance of a product/device after it is released for distribution.

The Sponsor's product in this registry contains both:

Biologic compound(s) and  
Device component(s) (pre-filled syringe, pen).

Complaints associated with any component of the Sponsor's product must be reported to the Sponsor. For adverse events, please refer to Sections 7.1 through 7.1.8. For product complaints, please refer to Section 7.2.

## **7.1 Medical Complaints**

### **7.1.1 Adverse Events**

#### **Adverse Events/Adverse Events of Special Interest Reporting:**

The Physician will monitor each patient from the time the applicable registry-specific parental informed consent/patient assent form (authorization form) is signed throughout the Registry participation for all Adverse Events as described in Section 6.6.5 (Safety Data Collection).

Follow-up contact can include a certified letter or phone call to the patient. All contact must be clearly documented in the patient's registry file.

All medications used to treat these events will also be captured. A complete list of the Adverse Events of Special Interest can be found in Section 7.1.3.

The Physician will assess and record the AE in detail including the date of onset, signs/symptoms, severity, time course, duration and outcome, relationship of the AE to treatment, an event diagnosis, if known, and any action(s) taken. For SAEs considered "possibly related," "probably not related" "and not related" to the registry treatment, the Physician will provide another cause of the event. For AEs to be considered sporadic, the events must be of similar nature and severity. SAEs or Adverse Events of Special Interest, whether in response to a query, observed by site personnel, or reported

spontaneously by the patient will be recorded. Information about medications taken for the SAE or the Adverse Event Special Interest will be collected.

All events reported throughout the patient's participation in the registry will be followed until satisfactory conclusion or until 70 days following the last registry dose (whichever is longer).

### **7.1.2 Adverse Event Definition**

An adverse event (AE) is defined as any untoward medical occurrence in a patient, which does not necessarily have a causal relationship with their treatment. An AE can therefore be any unfavorable and unintended sign (including an abnormal laboratory finding), symptom, or disease temporally associated with the use of a medicinal product, whether or not the event is considered causally related to the use of the product.

Such an event can result from use of the drug as stipulated in the labeling, as well as from accidental or intentional overdose, drug abuse, or drug withdrawal. Any worsening of a pre-existing condition or illness is considered an AE. Laboratory abnormalities and changes in vital signs are considered to be AEs only if they result in permanent or temporary discontinuation of treatment with Humira or MTX, necessitate therapeutic medical intervention and/or if the Physician considers them to be AEs.

An elective surgery/procedure scheduled to occur during the registry will not be considered a SAE if the surgery/procedure is being performed for a pre existing condition and the surgery/procedure has been pre planned prior to entry to the registry. However, if the pre existing condition deteriorates unexpectedly during the registry (e.g., surgery performed earlier than planned), then the deterioration of the condition for which the elective surgery/procedure is being done will be considered an AE.

### 7.1.3 Adverse Events of Special Interest

The Physician will monitor each patient for clinical and laboratory evidence for pre-defined Adverse Events of Special Interest at the Baseline visit and on a routine basis through Year 10 of the registry as mentioned in Section 6.5 Registry Duration.

AEs of Special Interest for this registry include:

Serious and nonserious opportunistic infections including the following bacterial, fungal, viral, and parasitic infections: Aspergillus, Blastomyces, Candida, Coccidioides, Cryptococcus, Cytomegalovirus, Histoplasma, Listeria, Nocardia, Paracoccidioides, Pneumocystis, Toxoplasma, Tuberculosis, Herpes, Bacillary angiomatosis, Mucormycosis, Progressive Vaccinia, Zygomycosis, BK virus, and JC virus.

Hypersensitivity reaction to Humira injection

Lymphoma

Hepatosplenic T-cell lymphoma

Non-melanoma skin cancer (NMSC)

Leukemia

Other malignancies (except lymphoma and NMSC)

Immune reactions including lupus, lupus-like reactions, and severe allergic reactions

CNS demyelinating disorders (including MS and Guillain-Barré syndrome and optic neuritis)

Hematologic events that are serious or lead to permanent discontinuation of treatment (e.g., aplastic anemia, granulocytopenia, granulocytes maturation Arrest, Leucopenia, Neutropenia, Pancytopenia, and Thrombocytopenia)

Hepatic events that are serious or lead to permanent discontinuation of treatment (e.g., persistent liver function test abnormalities, acute liver failure, and other serious hepatic events)

Vasculitis

Diverticulitis

Intestinal perforation

Congestive heart failure (CHF)

Severe CPK elevations (defined as CTC grade 3 and above) and associated clinical syndromes

New onset seizure disorders defined as any new epilepsy disorder diagnosed within the timeframe of the registry

Antiphospholipid syndrome and associated autoantibodies

New onset or worsening of Psoriasis

All events leading to premature discontinuation of treatment (Note: limited to only Adverse Events of Special Interest [listed above] leading to premature discontinuation for patients participating in the direct to HCP process)

All events that are probably or possibly related to treatment (Note: limited to only Adverse Events of Special Interest [listed above] that are probably or possibly related to treatment for patients participating in the direct to HCP process)

Antiphospholipid syndrome is defined as the presence of lupus anticoagulants (LA) or anticardiolipin antibodies (aCL) plus the presence of these antibodies in patients with arterial or venous thrombosis or pregnancy morbidity. At least one laboratory criterion and one clinical criterion must be present. Clinical criteria include objectively confirmed arterial, venous, or small-vessel thrombosis, or pregnancy morbidity consisting of recurrent fetal loss before the 10th week of gestation, 1 or more unexplained fetal death at or beyond the 10th week of gestation, or premature birth due to placental insufficiency, eclampsia, or preeclampsia. Laboratory criteria include medium or high titer Immunoglobulin G (IgG) or Immunoglobulin M (IgM) aCL or the presence of LA on 2 or more occasions at least 6 weeks apart.

Additional follow-up for the occurrence of malignancies and congestive heart failure is required annually for patients completing assessment through 5 years. Occurrence of malignancies and congestive heart failure will be collected for a total of 10 years starting from the registry entry date.

During the course of the registry additional Adverse Events of Special Interest may be identified by AbbVie. Updates to the Adverse Events of Special Interest will be maintained and collected through the eCRF system. Sites will be trained on all updates to the eCRF system.

The Physician will assess and record any additional information on the Adverse Events of Special Interest in detail on the Adverse Events of Special Interest eCRF.

The Physician will assess all reported Adverse Events of Special Interest for seriousness and follow the requirements/timelines for reporting any AEs of Special Interest that fulfills the criteria of an SAE, as defined in Section 7.1.4.

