## 6.0 Investigational Plan

Patients, who agree to participate in the registry, will be followed for up to 10 years (within a registry arm), including patients who discontinue Humira (monotherapy or combination therapy with MTX) or MTX (without Humira). For patients who switch from the MTX arm to the Humira arm, the 10-year follow-up period will start at the time of enrollment into the Humira arm. This registry will assess the incidence and rate of Humira (monotherapy or combination therapy with MTX) or MTX observational and treatment-emergent SAEs, Adverse Events of Special Interest (AESI) and Pregnancy in patients diagnosed with moderately to severely active polyarticular or polyarticular-course JIA through Year 5. AESI are listed in Section 7.1.4 of this protocol. Starting at Year 6, patients will be followed annually for SAEs, a subset of AESI that includes congestive heart failure (CHF), malignancies, AEs at least possibly related to and/or leading to discontinuation of registry treatment, and pregnancies through Year 10. For polyarticular JIA patients 2 to < 4 years of age in countries with available local approval for this group

of patients at the time of consent to the registry, SAEs, all AESI, and pregnancy (at the age when a patient can become pregnant) will be collected for the full 10 years.

Patients who have discontinued or will discontinue from the registry (prior to completion of 10 years) will be contacted to determine interest in enrollment into the direct to HCP (Health Care Provider) follow-up process as described in Section 6.2. AESI, hospitalizations, surgeries and death as listed in Section 7.1.3 and Section 7.1.4 will be collected through Year 5 for those patients who choose to participate in the direct to HCP follow-up process. Starting at Year 6, patients will be followed annually for congestive heart failure, malignancies, hospitalizations, surgeries, and death through Year 10. Any other AEs, SAEs, and/or pregnancies should be reported according to normal spontaneous reporting procedures, and they are not subject to the requirements of this protocol. In countries with available local approval at the time of consent, polyarticular JIA patients 2 to < 4 years of age who discontinue for any reason, will be offered the opportunity to participate in the direct to HCP follow-up process and will be followed for AESI, hospitalizations, surgeries, and death annually for the full 10 years.

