#### **6.5 Registry Duration**

The planned follow-up observation period is 10 years from enrollment into one of the treatment arms. The follow-up period for patients that switch from the MTX arm to the Humira arm will begin when they enroll into the Humira arm, in which case participation would be longer (i.e., up to 10 years from the time of the switch).

A patient may withdraw from the registry at any time without prejudice. If the physician decides it is in the best interest of the patient to discontinue Humira or MTX for any reason, treatment should be stopped. Physicians are encouraged to keep patients in the registry for a full 10-year observation period irrespective of future treatment decisions so important and complete safety and effectiveness information can be obtained. If the patient is not seen at a visit, efforts, i.e., phone, fax, letter, will be made to gather safety data through Year 10.

Patients in the MTX arm who are prescribed Humira treatment must be re-consented before enrolling in the Humira arm during the time that the enrollment period is open (i.e., until enrollment in the Humira treatment arm is complete).

If a patient withdraws or is withdrawn from the registry, this should be noted, along with the reason for withdrawal on the electronic study completion page. At the time of withdrawal from the registry, an assessment of the patient's current medical condition will be completed.

Patients who discontinue from the registry or transition to another HCP will be offered to participate in the direct to HCP follow-up process by their registry physician, as allowed

by applicable local regulations. If the patient (or Parent/Guardian for pediatric patients) agrees, a consent/assent and/or patient authorization for use/disclosure for data (as applicable) will be obtained.

Effectiveness measures will not be collected from patients participating in the direct to HCP process.

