#### **6.6.5 Safety Data Collection**

The following safety information will be collected from the time the parental consent and patient assent forms are signed: AEs of Special Interest and SAEs. The Physician will assess and record the AE in detail including the date of onset, description, severity, time course, duration and outcome, relationship of the AE to treatment, an event diagnosis, if known, and any action(s) taken. For SAEs considered "possibly related," "probably not related" and "not related" to the registry treatment, the Physician will provide the alternative etiology of the event. Information about medications taken to treat the SAE or the Adverse Event of Special Interest will be collected.

During the first 5 years of the registry, all available patient data, including SAEs, AESI as defined by the protocol and pregnancies will be collected at each doctor's visit. However, SAEs, AESI and pregnancy information can be collected at any time during the registry, not only at each doctor's visit. During Years 6 through 10 of the registry, patient data will be collected annually, including SAEs, a subset of AESI that includes congestive heart failure, malignancies, AEs at least possibly related to and/or leading to discontinuation of registry treatment, and pregnancies (Figure 1). Polyarticular JIA patients 2 to < 4 years of age, in countries with available local approval for this group of patients at the time of consent to the registry, will have SAEs, AESI, and pregnancy (potentially at the age when patient can become pregnant) collected for the full 10 years as defined by the protocol (Figure 2). Patients who develop an SAE or Adverse Events of Special Interest (AESI) while in the registry will be followed throughout the patient's participation in the registry until satisfactory conclusion or until 70 days following the last registry dose (whichever is longer).

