For patients participating in the HCP process, safety data will be collected by the participating HCP using the HCP questionnaire on an annual basis. The questionnaire to be used through Year 5 focuses on the collection of Adverse Events of Special Interest (AESI), hospitalizations, surgeries, and death. The questionnaire to be used for Years 6 through 10 focuses on collection of a subset of AESI that includes congestive heart failure and malignancies, hospitalizations, surgeries, and death (Figure 1). Polyarticular JIA patients 2 to < 4 years of age in countries with available local approval for this group, will have AESI, hospitalizations, surgeries and death collected for the full 10 years as defined by the protocol (Figure 2). The questionnaire may be completed by the registry physician or the patient's current HCP (if the patient is no longer under the care of a registry physician).

All patients who participate in or discontinue from the registry during the first 5 years will be followed for SAEs and AEs of Special Interest until satisfactory conclusion or for 70 days after their last dose of registry drug (whichever is longer) to further evaluate safety. All patients who participate in or discontinue from the registry during Years 6

through 10, will be followed for all SAEs, CHF and malignancies until satisfactory conclusion or for 70 days after last dose of registry drug (whichever is longer) to evaluate safety. All patients who participate in or discontinue from the direct to HCP follow-up process up through Year 5 will be followed for AESI, hospitalizations, surgeries and death until satisfactory conclusion or for 70 days after their last dose of registry drug (whichever is longer) to further evaluate safety. All patients who participate in or discontinue from the direct to HCP follow-up process up during Registry Year 6 through Year 10 will be followed for malignancies, CHF, hospitalizations, surgeries, and death until satisfactory conclusion or for 70 days after their last dose of registry drug (whichever is longer) to further evaluate safety ([Figure 1](#)).

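### For patients aged 4 to 17 the protocol states the Year 6–10 safety collection scope inconsistently, so it is unclear which non-serious AESI, other than CHF and malignancy, are collected and counted after Year 5

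*Supplement*

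**What the plan says.** All references are to the current protocol text, for patients aged 4 to 17 in the registry proper (not the direct-to-HCP process).

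- **Section 7.1.3, opening.** The physician monitors each patient for "pre-defined Adverse Events of Special Interest at the Baseline visit and on a routine basis through Year 10 of the registry". The sentence carries a pointer to Section 6.5 and has no age limit.
- **Section 6.5, the target of that pointer.** It says "The planned follow-up observation period is 10 years from enrollment into one of the treatment arms" and asks for efforts to gather safety data through Year 10, but gives no list of events by year.
- **Section 7.1.3, later paragraph on additional follow-up.** After Year 5 it names only malignancies and CHF.
- **Section 6.0.** From Year 6 the list holds pregnancies, SAEs and also "a subset of AESI that includes congestive heart failure (CHF), malignancies, AEs at least possibly related to and/or leading to discontinuation of registry treatment". Table 1 note f and Section 7.1.7 give the same list, as does the second paragraph of Section 6.6.5, which ends with "AEs at least possibly related to and/or leading to discontinuation of registry treatment, and pregnancies".
- **Section 6.6.5, fourth paragraph.** Everyone who participates in or leaves the registry in Years 6–10 "will be followed for all SAEs, CHF and malignancies", until conclusion or 70 days after last dose.
- **Section 6.7.2, patients who stopped treatment.** From Year 6, "patients will be followed annually for the subset of AESI which include congestive heart failure and malignancies and SAEs through Year 10".
- **Section 6.8.1, on stopping treatment.** All patients are to be followed "from Year 6 through Year 10 congestive heart failure, malignancies, pregnancies and SAEs".

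Two other places bear on the point. Section 7.1.7 opens by making AESI reportable at any time after the last dose if the physician thinks them related to MTX or Humira. Section 10.3.1 reports AESI rates per 100 patient-years of observation from first day to last contact, with no change of event list or denominator at Year 5.

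**The concern.** Long-term safety is the primary objective, and Years 6–10 are half of the planned follow-up. Take a non-serious herpes infection, which falls under the AESI list, in Year 7 in a 14-year-old. If judged unrelated and not treatment-ending, it is within scope under the opening of Section 7.1.3 and outside it under Section 6.0. If judged possibly related, it is within scope under Section 6.0 and missing from the lists in the fourth paragraph of 6.6.5, in 6.7.2 and in 6.8.1.

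The cross-references do not settle the matter. Section 7.1.1 sends the physician to Section 6.6.5 for what to monitor, and that section holds both the longer and the shorter list.

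For patients off drug there is a further clash. Sections 6.7.2 and 6.8.1 do not name related non-serious events, while the opening of Section 7.1.7 requires related AESI to be reported without a time limit.

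Two things are at stake: which late non-serious AESI enter the database, and whether a rate to last contact divides events from one period by patient-years from a longer one.

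**Working it through.** The plan states no figure for this point, so the check is mainly a comparison of texts.

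**Step 1. Is an event in Years 6–10 within scope (age 4 to 17, in the registry)?**

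| Event | 7.1.3 opening | 6.0, 6.6.5 para 2, 7.1.7, Table 1 note f | 6.6.5 para 4, 6.7.2, 6.8.1 |
|---|---|---|---|
| SAE, including serious AESI | yes (SAEs via 7.1.4, through Year 10) | yes | yes |
| CHF, malignancy | yes | yes | yes |
| Other non-serious AESI, at least possibly related or treatment-ending | yes | yes | not named |
| Other non-serious AESI, neither related nor treatment-ending | yes | no | not named |

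The first two rows agree throughout; the last two do not. Pregnancies appear in some lists only, but Section 7.1.9 sets their collection period separately, so they are not in doubt.

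**Step 2. Can the opening of 7.1.3 and Section 6.0 both be meant?** Section 6.0 sets out collection of all AESI for the full 10 years as a separate rule for ages 2 to <4. If the opening of 7.1.3 meant the same for everyone, that rule would be redundant. The two therefore differ in substance.

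**Step 3. What could the rate in Section 10.3.1 lose?** This is an illustration. Assumptions: a constant event rate, and an AESI type not captured at all after Year 5 while its patient-years stay in the denominator.

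- Years 1–5, Humira arm: 500 × 5 = 2500 patient-years, matching the maximum in Section 10.6.
- Years 6–10: a fraction f of a further 2500 patient-years is observed. The documents do not give f, so a range is shown.
- Reported rate ÷ true rate = 2500 / (2500 + 2500 f) = 1 / (1 + f).

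| f | Reported ÷ true |
|---|---|
| 0.25 | 2500/3125 = 0.80 |
| 0.50 | 2500/3750 = 0.67 |
| 0.75 | 2500/4375 = 0.57 |
| 1.00 | 2500/5000 = 0.50 |

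If all AESI are collected to Year 10, the ratio is 1. For most AESI types the true loss would be smaller than in the table, because serious events are still collected and, under the longer list, so are related and treatment-ending ones. The table is the limiting case.

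**The case against.** The case for calling this tidying-up is substantial, and much of it stands.

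- **The intended rule can be inferred.** The longer list stands in four places, including the activities table. That makes the repair easy but leaves the contrary sentences in force.
- **The opening of 7.1.3 is weak as a collection rule.** It speaks of monitoring, it also covers ages 2 to <4, and the same section later names only malignancies and CHF. It should not be read as a clear demand for all AESI to Year 10 at ages 4 to 17.
- **The short lists are not all of one kind.** The sentence in the fourth paragraph of 6.6.5 is partly a rule for following events to conclusion, and the wording in 6.7.2 need not be exhaustive. Still, 6.7.2 speaks of annual follow-up and 6.8.1 of following all patients, which read as scope.

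A reader might go further in three ways that the documents do not support.

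- *That late data cannot be restricted to comparable events.* They can: SAEs, CHF and malignancies are common to all main versions. That core includes serious infections, on which Section 10.6 bases the sample size, and the malignancies and CHF for which it adds five years. The price of that restriction is dropping the related and treatment-ending events that four places say are collected.
- *That related events off drug are not sought.* The opening of Section 7.1.7 makes related AESI reportable at any time after the last dose, and treatment-ending events cannot arise once treatment has ended. What remains is a conflict between that sentence and Sections 6.7.2 and 6.8.1, not an established gap in ascertainment.
- *That sites do record differently.* Section 7.1.3 has AESI updates maintained through the eCRF system and sites trained on them, which may standardise capture. The forms are not in the documents.

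**Conclusion.** The inconsistency is real and stands in the current text. It concerns Years 6–10, ages 4 to 17, and only non-serious AESI other than CHF and malignancy. Within that group, events neither related nor treatment-ending are in scope under the opening of 7.1.3 and out of scope elsewhere. Related or treatment-ending events are in scope under the longer list and not named in the shorter ones. Serious events, CHF and malignancies are not in doubt.

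The effect on reported rates is conditional. Under the stated assumptions the limiting dilution is to 0.80–0.50 of the true rate; how much would occur depends on late retention, on the share of events no longer collected, and on what the eCRF asks for, none of which is given. Figure 1, to which Section 6.6 points, was not available to this check. It might confirm one list but would not remove the conflicting sentences. Differences between sites are a possibility, not a finding. The point deserves correction because it touches the primary safety objective and the repair is cheap.

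**What to change.** Reconcile the passages to one Year 6–10 list, the one already in Section 6.0, the second paragraph of 6.6.5, Section 7.1.7 and Table 1 note f, for patients on and off drug alike. Five places need amending:

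1. Section 7.1.3, opening: refer to that list for ages 4 to 17 after Year 5, and replace the pointer to Section 6.5.
2. Section 7.1.3, paragraph on additional follow-up: align with the list.
3. Section 6.6.5, fourth paragraph: refer to the list.
4. Section 6.7.2: the same, consistent with the opening of Section 7.1.7.
5. Section 6.8.1: the same.

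Keep two exceptions explicit: patients aged 2 to <4 have all AESI collected for 10 years, and the direct-to-HCP process has its own list.

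In Section 10.3.1, for AESI types not on the Year 6–10 list, limit both events and patient-years to Years 1–5 for patients aged 4 to 17, so that rates to last contact are not diluted. If a separate SAP already sets such a window, a cross-reference is enough.

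Cost: wording in five places, one analysis rule and an eCRF guidance note. No new data collection is needed beyond what those four places already require.
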